11.4.2.2. ACUITY X4 Pooling of Cohorts

It is expected that results will not differ [REDACTED] for any endpoint, with the exception of Secondary Effectiveness Endpoint 2. In order to confirm the poolability for each endpoint, a pooling analysis will be performed. Specifically, a likelihood ratio test from a regression model will be conducted. The type of regression model used for each of the following endpoints is as follows:

- Primary Safety Endpoint (CFR from Implant to 6 Months): Logistic Regression
- Primary Effectiveness Endpoint 1 (Pacing Threshold at 3 Months, programmed): Logistic Regression
- Primary Effectiveness Endpoint 2 (Pacing Threshold at 3 Months, best proximal): Logistic Regression
- Secondary Effectiveness Endpoint 1 (Sensed Amplitude at 3 Months): Linear Regression
- Secondary Effectiveness Endpoint 2 (Pacing Impedance at 3 Months): Linear Regression

December 17, 2013
FINAL

Boston Scientific
NAVIGATE X4 Study Protocol
90874504 Version AB
Page 65 of 101

The regression model will include additional baseline covariates to attempt to adjust for any imbalances between baseline data. The following baseline covariates will be considered: age, gender, etiology, CRT-D indication, LVEF, NYHA classification, medications, arrhythmia history, associated diseases/risk factors, height, weight and geography. [REDACTED]

[REDACTED].

[REDACTED]

11.4.2.3. Pooling of Geographies

It is expected that results will not differ by geographic regions for any of the endpoints for either lead. In order to confirm the poolability of the data from the geographic regions for each endpoint, a pooling analysis will be performed. Specifically, a likelihood ratio test from a regression model will be conducted. [REDACTED]

[REDACTED]

11.4.2.4. Pooling of investigational centers

Center-to-center heterogeneity will be assessed for each endpoint by performing random effects regression analyses. Centers with less than five enrollments will be combined to form “supercenters”. Small centers will be combined until the newly created supercenter has five enrollments, and then a new supercenter will be created. The following regression models for each of the following endpoints will be used:

ACUITY X4

- Primary Safety Endpoint (CFR from Implant to 6 Months): Random Effects Logistic Regression
- Primary Effectiveness Endpoint 1 (Pacing Threshold at 3 Months, programmed): Random Effects Logistic Regression
- Primary Effectiveness Endpoint 2 (Pacing Threshold at 3 Months, best proximal): Random Effects Logistic Regression
- Secondary Effectiveness Endpoint 1 (Sensed Amplitude at 3 Months): Random Effects Linear Regression
- Secondary Effectiveness Endpoint 2 (Pacing Impedance at 3 Months): Random Effects Linear Regression

RELIANCE 4-FRONT

- Primary Safety Endpoint 1 (CFR from Implant to 3 Months): Random Effects Logistic Regression

December 17, 2013
FINAL

Boston Scientific
NAVIGATE X4 Study Protocol
90874504 Version AB
Page 66 of 101

- Primary Safety Endpoint 2 (CFR from 3 to 24 Months): Random Effects Logistic Regression
- Secondary Safety Endpoint (Detection of VT/VF): Random Effects Linear Regression
- Primary Effectiveness Endpoint (Pacing Threshold at 3 Months): Random Effects Linear Regression
- Secondary Effectiveness Endpoint 1 (Sensed Amplitude at 3 Months): Random Effects Linear Regression
- Secondary Effectiveness Endpoint 2 (Pacing Impedance at 3 Months): Random Effects Linear Regression
- Secondary Effectiveness Endpoint 3 (VT/VF Shock Conversion): Random Effects Logistic Regression

Investigational center will be added into the model as a random effect. Centers will be deemed to be heterogeneous if the variance of the random center effect is found to significantly differ from zero. A significance level of ■% will be used for each test. If it determined that the center random effect is significant for an endpoint, then the results from the random effects model for that endpoint will be presented. Regardless of the results of the random effects model, results by investigational center will be presented for each endpoint.

11.4.3. Subgroup Analyses

Analyses will be performed for each endpoint to determine whether significant differences exist in endpoint results between subgroups. Results will be presented for each subgroup, regardless of whether significant differences exist between the subgroups. The list of baseline covariates (with applicable subgroups in parentheses) includes, but is not necessarily limited to:

- Sex (Female vs. Male)
- Geography (International vs. United States)
- Age (< 65 years vs. ≥ 65 years)
- NYHA Class
- LVEF (< 25% vs. ≥ 25%)
- QRS width (< 150 ms vs. ≥ 150 ms)
- Bundle Branch Block Morphology (LBBB vs. non-LBBB)

For ACUITY X4, the following additional baseline covariates will be assessed:

- Spiral length (Short vs. Long)
- Lead shape (Spiral vs. Straight)

For RELIANCE 4-FRONT, the following additional baseline covariates will be assessed:

- Fixation type (Active vs. Passive)
- Coil type (Dual vs. Single)

December 17, 2013
FINAL

Boston Scientific
NAVIGATE X4 Study Protocol
90874504 Version AB
Page 67 of 101

The baseline covariate will be added to a univariate regression model and a test for significance at the █% level will be performed. The regression models used for each endpoint will be identical to those specified in Section 11.4.2.1.

In addition to subgroup analyses, descriptive statistics of patient demographic and baseline characteristics will be presented for each subgroup listed in this section. Descriptive statistics will also be presented for the overall study population.

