11.4.2. Pooling Analyses

11.4.2.1. RELIANCE 4-FRONT Pooling of Cohorts

It is expected that results will not differ [REDACTED] for any endpoint, with the exception of Secondary Effectiveness Endpoint 2. In order to confirm the poolability for each endpoint, a pooling analysis will be performed. Specifically, a likelihood ratio test from a regression model will be conducted. The type of regression model used for each of the following endpoints is as follows:

- Primary Safety Endpoint 1 (CFR from Implant to 3 Months): Logistic Regression
- Primary Safety Endpoint 2 (CFR from 3 to 24 Months): Logistic Regression
- Secondary Safety Endpoint (Detection of VT/VF): Linear Regression
- Primary Effectiveness Endpoint (Pacing Threshold at 3 Months): Linear Regression
- Secondary Effectiveness Endpoint 1 (Sensed Amplitude at 3 Months): Linear Regression
- Secondary Effectiveness Endpoint 3 (VT/VF Shock Conversion): Logistic Regression

The regression model will include additional baseline covariates to attempt to adjust for any imbalances between baseline data. The following baseline covariates will be considered: age, gender, etiology, CRT-D indication, LVEF, NYHA classification, medications, arrhythmia history, associated diseases/risk factors, height, weight and geography. [REDACTED]

[REDACTED]

[REDACTED]

[REDACTED]

[REDACTED]

[REDACTED]

[REDACTED]

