11.4.4. Multivariate Analyses

Univariate analyses of various baseline covariates and their relationship to each endpoint are outlined in Section 11.4.3. For each endpoint, all baseline characteristics found to be significantly associated with the outcome will be included as covariates in a multivariate regression model. The impact of each baseline characteristic’s subgroups will be presented along with the multivariate model results.

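### Geography varies only between centres, but Protocol 11.4.3 tests it in a subject-level model with no centre term, so any centre-to-centre variation pushes the false-positive rate above the stated level by an unknown amount

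*Protocol*

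**What the plan says.** - Protocol 11.4.3 includes "Geography (International vs. United States") in the list of subgroup factors for both leads. The test for each factor is: "The baseline covariate will be added to a univariate regression model and a test for significance". The level is redacted.
- On model type, 11.4.3 states: "The regression models used for each endpoint will be identical to those specified in Section 11.4.2.1". That section lists RELIANCE 4-FRONT models such as "Primary Safety Endpoint 1 (CFR from Implant to 3 Months): Logistic Regression" and "Primary Effectiveness Endpoint (Pacing Threshold at 3 Months): Linear Regression". The ACUITY X4 list in 11.4.2.2 is of the same kind. Neither list names a centre term.
- Protocol 11.4.4 uses the result by rule: "all baseline characteristics found to be significantly associated with the outcome will be included as covariates in a multivariate regression model". No centre term is named there either.
- Protocol 11.4.2.4 is a separate check for centre heterogeneity, run for each endpoint: "Investigational center will be added into the model as a random effect". If centres prove heterogeneous, that model's results are shown for the endpoint. Nothing extends this to the geography test or to 11.4.4.
- Protocol 11.4.2.3, on pooling of regions, says that "a likelihood ratio test from a regression model will be conducted". The text that follows is redacted.

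**The concern.** A subject's region is settled by the centre that enrols the subject. The comparison is therefore one group of centres against another, and its precision depends largely on how many centres are on the smaller side. A regression that counts every subject as an independent observation of geography ignores the part of the variance that subjects at one centre share.

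The plan takes clustering seriously enough to fit a random centre effect for every endpoint, yet does not use it for this factor, which differs only between centres. Sex, age, LVEF and QRS width vary within centres and are much less affected.

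At stake is a chance mix of better or worse implanting centres abroad being reported as a regional difference in lead performance, and then being kept in the multivariate model because it reached significance.

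**Working it through.** The documents state no error rate for this test, so there is no planned figure to reproduce.

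**Inputs from the documents**
- Up to 125 centres in the US, Israel and Canada (Protocol synopsis and 7.1).
- Enrolment of 1542 to 2290 (Protocol 7.1), with about 1840 expected (9.4).
- ACUITY X4 dataset of 748, that is 534 + 214 (SAP 2.1).

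**Assumptions, because the documents give no figure**
- ICC of 0.01 to 0.05; 15 of the 125 centres international.
- Test level 5%, with 15% as an alternative.
- Coefficient of variation (cv) of centre size 0 or 0.8.
- No true geography effect.
- The enrolment figures stand in for analysed subjects. Analysed numbers will be lower for some endpoints.

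**Formula**
- Mean centre size m = N/125.
- Design effect DEFF = 1 + ((1 + cv²)·m − 1)·ICC.
- Actual error rate = 2·(1 − Φ(z/√DEFF)), with z = 1.96 at the 5% level.

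**Worked case.** N = 1840 gives m = 14.72. With ICC 0.05 and equal centres, DEFF = 1 + 13.72 × 0.05 = 1.686 and √DEFF = 1.298. Then 1.96/1.298 = 1.51, and the two-sided tail is 13.1%.

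**Results at a 5% level (cv 0 to cv 0.8)**

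| N | m | ICC 0.01 | ICC 0.02 | ICC 0.05 |
|---|---|---|---|---|
| 748 | 5.98 | 5.6% to 6.0% | 6.2% to 7.1% | 8.0% to 10.3% |
| 1542 | 12.34 | 6.3% to 7.3% | 7.7% to 9.6% | 11.7% to 16.2% |
| 1840 | 14.72 | 6.6% to 7.7% | 8.3% to 10.5% | 13.1% to 18.2% |

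At a 15% level and ICC 0.05, the same formula gives 19.8% to 23.0% (N = 748) and 26.8% to 32.7% (N = 1840). The ratio to the nominal level is therefore smaller.

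**Simulation, continuous endpoint** (125 centres, 15 international, t-test at 5%, 4,000 runs per cell). At ICC 0.05, cv 0 and cv 0.8 gave 8.5% and 9.9% (N = 748), 11.8% and 15.9% (N = 1542), and 13.1% and 18.0% (N = 1840). At ICC 0.01 to 0.02 all cells lay between 4.9% and 10.6%. Other runs under similar assumptions put the N = 748, ICC 0.05 figure anywhere from about 7% to 12%.

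**Simulation, binary endpoints** (ordinary logistic likelihood ratio test at 5%, ICC on the latent scale, 6,000 runs per cell)
- Assumed 3% complication rate, N = 1542 to 1840, ICC 0.02 to 0.10: 5.3% to 8.7%. With ICC 0 the same test gave 4.7% to 5.8%, so little of this comes from clustering unless the ICC is near 0.10.
- 25% non-responders (the complement of the 75% performance goal), N = 748, ICC 0.05: 6.8% (equal centres) and 8.6% (cv 0.8).

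**Effect of a centre term** (continuous endpoint, cv 0.8, N = 748 and 1840, 6 or 15 international centres, ICC 0.02 to 0.10). A random-centre model with centre-level degrees of freedom gave 4.6% to 6.0% at the 5% level. On the same data the model without the centre term gave 6.8% to 27.4%.

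**The case against.** The strongest reply has four parts.

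1. **The size is assumed.** ICC, country split and test level are all missing or redacted. A reader might infer that false geography findings occur two to three times as often as stated for every endpoint. The documents do not support that. With equal centres and a 5% level it needs an ICC of about 0.03 to 0.06 at roughly 15 subjects per centre. It does not describe the 748-subject dataset at low ICC, a 15% level, or rare complications. A much higher figure for the safety endpoints can be produced by letting complication rates vary on the probability scale with ICC 0.05. At a mean of 3%, however, that implies a between-centre SD of √(0.03 × 0.97 × 0.05) = 3.8 percentage points, more than the mean itself. This part of the reply stands, and the size is stated conditionally for that reason.
2. **The pooling decision is out of sight.** A reader might also infer that the regional poolability test in 11.4.2.3 is defective. Its model, level and consequence are redacted, so a centre term there cannot be ruled out. This stands.
3. **Stakes are limited.** Under 11.3.1, success rests on the primary endpoints. Subgroup results are shown whether or not they are significant, and by-centre results are always presented. The visible error is a false alarm about geography, not a false claim of safety or effectiveness. This stands too.
4. **The plan already models centre.** It does, in 11.4.2.4, but only as a heterogeneity check and an alternative presentation of the endpoint. It never reaches the geography test, so this part does not answer the concern.

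It is also fair that random-intercept logistic models may fit poorly with sparse events. At 748/125 ≈ 6 subjects per centre and an assumed 3% rate, there are about 0.2 events per centre.

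**Conclusion.** The concern holds in a limited form. The readable text of 11.4.3 tests a centre-level factor with subject-level standard errors, and 11.4.4 acts on the result. For any positive centre variance the standard error is too small and the error rate is above nominal. That direction does not depend on the redactions; only the size does.

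For continuous endpoints, assuming a 5% level, 125 centres and 15 international, the rate is about 5% to 10% at ICC 0.01 to 0.02. At ICC 0.05 it is about 7% to 12% (N = 748) or 12% to 18% (N = 1542 to 1840). Since 125 is a maximum, fewer centres at the same enrolment would raise these figures. For rare complications the excess may be small. The consequence is confined to the reported geography subgroup finding and the choice of covariates in 11.4.4. It is worth correcting because the remedy is already named in the plan.

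**What to change.** **Change**
- In 11.4.3, for Geography only, replace the univariate model with the random-effects linear or logistic model already named in 11.4.2.4. Enter geography as a fixed effect and centre as a random intercept. Use actual centres, or supercenters formed within one country so that none mixes regions.
- Specify small-sample degrees of freedom (for example Kenward-Roger for the linear models, or between-within), because international centres may be few.
- Where events are too sparse for the random-intercept logistic model, use a centre-clustered test with a small-sample correction.
- In 11.4.4, admit geography on the centre-adjusted test, and include the random centre intercept whenever geography is in the model.
- Apply the same to 11.4.2.3 only if its redacted model has no centre term.
- Leave the patient-level subgroup factors as they are.

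**Cost.** A short SAP addition and some programming, including the sparse-event fallback. The geography comparison will have less apparent power, because its real replication is the number of international centres. Enrolment, data collection, primary tests and success criteria do not change.

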11.4.4. Multivariate Analyses

Univariate analyses of various baseline covariates and their relationship to each endpoint are outlined in Section 11.4.3. For each endpoint, all baseline characteristics found to be significantly associated with the outcome will be included as covariates in a multivariate regression model. The impact of each baseline characteristic’s subgroups will be presented along with the multivariate model results.

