10.11. Source Documents from All Study-Required Visits

Table 10 below summarizes the source data requirements for this clinical study. Original source documents are required to be retained at the center. On the rare occasion where the original is not available, copies of the original source document must be signed and dated by a member of the investigational center team with a statement that it is a true reproduction of the original source document.

Table 10: Source Documentation Requirements

Requirement	Visit	Disposition
Informed consent documentation process	Enrollment	Retain at Center
Assessment of pregnancy for women of child bearing potential: method of assessment per physician discretion	Enrollment	Retain at Center
Documentation of the following: 
 • Demographics: age at implant, gender • Heart Failure assessment: LVEF, QRS width, GDMT • Vital signs: heart rate, blood pressure • Class I/III Antiarrhythmic medications • Subject’s height and weight • Arrhythmia history • Cardiac disease history 	Enrollment	Retain at Center
Documentation of the following: 
 • Time of first incision • Time of pocket closure, to document time 0 • Class I/III antiarrhythmic medications that the subject is prescribed prior to, but not including the implant procedure • Model and serial number of implanted cardiac devices • Manufacturer and model number of PSA 	Implant	Retain at Center
Printout of ACUITY X4 PSA measurements or signed Implant Technical Source Form	Implant	Retain at Center
Printout of PG measurements (sensed amplitude, pacing impedance, shock lead impedance, and pacing capture threshold results) either from PRM printout or a signed Technical Source Form (from applicable visit)	Implant, Follow-ups	Retain at Center
Printout of ECG strip (from PRM) documenting LOC for all implanted leads threshold tests	Implant, Pre-Discharge, 3-Month Follow up	Retain at Center

December 17, 2013
FINAL

Boston Scientific
NAVIGATE X4 Study Protocol
90874504 Version AB
Page 46 of 101

Table 10: Source Documentation Requirements

PA and lateral chest X-ray or fluoroscopic image of ACUITY X4 and RELIANCE 4-FRONT (as applicable) Lead distal tip fixation	Implant or Pre-Discharge	Retain at Center
Real time programmer/ PRM strip documenting induced VT/VF (if conducted and strip available)	Implant through 30 days post-implant	Retain at Center

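### Choosing covariates for the multivariate models by univariate significance exaggerates weak effects on the low-event endpoints, and no correction is planned

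*Protocol*

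**What the plan says.** Protocol section 11.4.3 lists seven baseline covariates common to both leads and two more for each lead, so nine per lead. The list is open: it "includes, but is not necessarily limited to" those named. For each endpoint, "The baseline covariate will be added to a univariate regression model and a test for significance at the" level that is blacked out in the public copy. Results are shown for every subgroup, significant or not.

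Section 11.4.4 then states that "all baseline characteristics found to be significantly associated with the outcome will be included as covariates in a multivariate regression model", and that the impact of each characteristic's subgroups is presented with the model. It names no effect measure or interval, and no shrinkage, resampling or other allowance for selection. SAP section 1 says the protocol holds everything needed for the analyses, and SAP section 2 adds nothing on this model.

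Three of the nine covariates are measured quantities with a stated cut: "Age (< 65 years vs. ≥ 65 years"), "LVEF (< 25% vs. ≥ 25"%), and QRS width at 150 ms. Protocol Table 10 requires source documentation of "Heart Failure assessment: LVEF, QRS width, GDMT" and of age at implant. NYHA class is listed without a grouping.

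**The concern.** Testing each factor alone, keeping those that pass, and refitting the survivors on the same data means that a weak factor is presented mainly when chance has enlarged its estimate. The usual standard errors take no account of this. A null factor that enters has done so only because its estimate happened to be far from zero.

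At stake is how the adjusted results are read. They would appear in the clinical report as the factors that matter for each endpoint, and for the primary safety endpoints those factors include lead shape, fixation type and coil type. A reader could take a modest or chance difference between lead designs or patient groups for a substantial one.

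**Working it through.** The plan gives no power, coverage or effect size for this analysis, so there is no figure to reproduce.

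**Inputs from the documents.** Nine listed covariates per lead (protocol 11.4.3). 748 subjects for ACUITY X4 (SAP 2.1, possibly somewhat more under its enrolment-date rule). 1,876 leads for RELIANCE 4-FRONT (SAP 2.2). Logistic regression for the safety endpoints (protocol 11.4.2.1 and 11.4.2.2).

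**Assumed.** Event rates of 6% and 12% (ACUITY X4) and 3% (RELIANCE 4-FRONT), that is 748 × 0.06 = 45, 748 × 0.12 = 90 and 1,876 × 0.03 = 56 events. Screening levels of 5% to 20%. The effect sizes below.

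**Step 1, chance entry.** With nine independent null covariates, the chance that at least one enters is 1 − (1 − α)^9: 37% at a 5% screen, 61% at 10%, 77% at 15%.

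**Step 2, one factor in isolation.** Let its test statistic be z ~ N(d, 1), kept if |z| > c. Coverage of the usual 95% interval, given selection, is P(|z − d| < 1.96 and |z| > c) / P(|z| > c). Exaggeration is the mean of |z| among kept results, divided by d.

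- Null factor (d = 0): 0% at a 5% screen, 0.05/0.10 = 50% at 10%, 0.10/0.15 = 67% at 15%, 0.15/0.20 = 75% at 20%.
- Real factor at a 5% screen:

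| Power of the univariate test | d | Coverage if kept | Exaggeration |
|---|---|---|---|
| 10% | 0.65 | 70% | 3.7 |
| 20% | 1.11 | 87% | 2.3 |
| 50% | 1.96 | 95% | 1.4 |
| 80% | 2.80 | 97% | 1.13 |

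The shortfall in coverage is confined to null and weakly powered factors.

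**Step 3, the two-step plan simulated.** Nine independent binary factors, four real and five null; univariate Wald screen; joint logistic model of the survivors; 95% Wald intervals. Ranges run over the three event settings.

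| True odds ratio of real factors | Coverage, all presented factors, 5% screen | Same, 15% screen | Median inflation of real log odds ratios |
|---|---|---|---|
| 1.25 | 47-63% | 76-83% | 2.0-3.3 |
| 1.5 | 77-85% | 86-90% | 1.3-1.9 |

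The unscreened nine-factor model covers 94-96%. Real factors with odds ratios of 1.5 or more are covered 92-98% even after screening. Real factors near 1.25 are covered about 73-84% at a 5% screen.

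**Step 4, where it matters less.** These runs used eight correlated binary covariates with effects from null to strong, and a 5% screen. Overall coverage was 89% for a logistic endpoint with 748 subjects and 10% events, and 92% with 25% events (the non-responder share at the ACUITY X4 effectiveness goal). For linear endpoints it was 93% with 748 and 95% with 1,876. The log odds ratio for a true odds ratio of 2.5 was 1.0 to 1.1 times the truth.

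**Step 5, cut-points (secondary).** For a normal covariate with a linear gradient, splitting it at proportion p keeps φ(z)²/(p(1 − p)) of the information: 0.637 at p = 0.5 and 0.490 at p = 0.2. Power of 80% becomes Φ(2.80 × √0.637 − 1.96) = 61%, or Φ(2.80 × √0.490 − 1.96) = 50%.

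**The case against.** The strongest reply is that little turns on this model. Protocol 11.3.1 ties success to the primary endpoints. The question of which subgroups differ belongs to 11.4.3, which shows all its results whether significant or not, so an unselected set stands beside the model. This stands, and it limits the weight of the point. Those results are unadjusted, however, and do not correct the multivariate estimates.

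A reader might infer that the reported effects are exaggerated throughout and that their intervals cover far less than 95% of the time. The documents do not support that. No 95% interval is promised in 11.4.4, the screening level is blacked out and a looser one shrinks the problem, and strong effects and linear endpoints are nearly unaffected. Much of the pooled shortfall comes from null factors that passed the screen, so it partly restates the false-positive rate.

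A reader might also infer that screening leaves confounding by masked factors. That is possible in principle, but the step 3 factors were independent, so no size can be given.

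Nor does the text settle that the cut forms of age, LVEF and QRS width enter the regression. Section 11.4.3 lists subgroups in parentheses and then speaks of adding the covariate. Only three of nine factors are concerned, the information-loss figures assume normality, and eligibility truncates LVEF at 35%. Cutting is a separate matter from selection.

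**Conclusion.** The point holds in a limited form. The rule in 11.4.4 selects on significance and refits on the same data without correction, and the SAP does not repair it. For null and weak factors on the low-event binary endpoints, which include the primary safety endpoints, presented effects will be materially too large and any 95% intervals will under-cover, to the extent shown in step 3.

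That size rests on assumed event rates, effects, subgroup shares and screening levels. The existence of the selection effect does not. The consequence is a risk of misreading a supportive analysis, with no effect on the endpoint tests. It is still worth changing, because the better model needs only data already collected.

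**What to change.** In 11.4.4, or by SAP addendum:

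- Fit one pre-specified model per endpoint with all the covariates named in 11.4.3 and no univariate screening. Fix the NYHA grouping in advance, and report any covariate added under the open list separately.
- Use Firth-type penalised logistic regression where events are few. At 45 events and nine factors there are only 5 events per factor. The 94-96% coverage quoted is for the unpenalised full model; the penalised version was not simulated.
- For ACUITY X4, code lead shape and spiral length as one three-level tip factor (straight, short spiral, long spiral). Spiral length is undefined for straight leads, so entering both terms would drop those leads (214 in SAP 2.1) or leave the model inestimable.
- Label the model exploratory.
- As a secondary change, state that age, LVEF and QRS width enter the model as continuous values, and keep the cut-points for the subgroup tables.

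The cost is a wording change, slightly more analysis work, and somewhat wider intervals for the factors that screening would have selected. No new data are needed.
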